In all ED studies that have been conducted for acute upper gastrointestinal hemorrhage, VCE has performed well when it travels through the pylorus. However, several high-risk lesions were missed if the VCE did not travel through the pylorus before the battery expired. The time to pass the pylorus is variable. At 60 minutes, 98% of capsules visualize the duodenum [6]; when the battery life is only approximately 20-30 minutes, approximately 50% visualize the duodenum (12/25 [7], 44/83 [8], and 7/12 [14]). In one study, the single missed active bleeding occurred in a patient who was bleeding in the post-pyloric duodenum and in whom the VCE battery expired before reaching the post-pyloric region [7]. For standard EGD, the use of pro-kinetic agents such as erythromycin or metoclopramide has improved mucosal visualization and has been increasingly used before the procedure. This strategy, combined with 60 minutes of visualization, will likely increase the accuracy of VCE as well.

The cost of the VCE is an important factor that affects future use in the ED. The physician Medicare national average fee is \$705 for the PillCam UGI and \$50 for the professional fee. Although expensive, VCE may be cost-effective if it safely reduces hospital admissions or emergency EGD. For comparison, in 2011, 236,000 patients received an EGD (International Classification of Diseases, Ninth Revision code 45.13) in the hospital for an upper UGIB, the median length of stay was 4.0 days, and the median charges were \$23,549.17 [12].

A decision-analytic model showed that VCE is cost effective for low- to moderate-risk patients despite increased upfront costs compared with clinical decision rules or nasogastric tubes. The use of VCE in the ED can potentially lead to more patients being safely discharged from the ED. The hospital admission is the single most expensive decision made by an emergency physician. Chandran et al [8] showed that the higher sensitivity of VCE compared with the Glasgow-Blatchford Score would have saved \$1691 per VCE by increasing the number of patients who could receive an outpatient EGD.

Currently, the VCE does not replace the need for traditional EGD when hemostasis or biopsy is needed. Technological advancements may allow a VCE operator to control movement of the capsule, collect biopsy samples, and perform therapeutic functions.

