### 3 OBJECTIVES

#### 3.1 Study Objectives

Our primary goal is to test whether ED Video Capsule Endoscopy (VCE) is able to safely discharge low risk patients for outpatient evaluation and management. Our secondary objective is to estimate the sensitivity and specificity of VCE compared to subsequent EGD in the detection of serious bleeding lesions in the upper gastrointestinal (GI) tract.

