#### 3.2 Study Outcome Measures

3.2.1 Primary Outcome: (1) Percent Discharged Home. Assumption is that 100% of Active Control (AC) group will be admitted.

3.2.2 Secondary Outcome: Sensitivity and specificity of VCE compared to EGD. *Endpoints will be defined in the following way:*

Positive Video Capsule Endoscopy will be defined as:

1. Fresh blood or evidence of active bleeding visualized in upper GI tract.
2. Coffee ground blood visualized in upper GI tract, but no active bleeding seen.
3. A High Grade Non-Variceal Lesion (Forrest Ia, Ib, IIa or IIb).
4. Signs of Variceal Hemorrhage.
5. Signs of malignancy visualized in upper GI tract.

Negative VCE:

5. Clean stomach and duodenum, no fresh blood or coffee ground.
6. Upper GI pathology non-causative/ incidental.
7. A low grade non-Variceal lesion (Forrest IIc, III).

An Inconclusive VCE:

8. Any capsule that does not pass the pylorus before battery life is expired (and does not detect lesion in stomach or esophagus).

Positive EGD

1. Fresh blood or evidence of active bleeding.
2. Coffee ground but no active bleeding seen.
3. A High Grade Non-Variceal Lesion (Forrest Ia, Ib, IIa or IIb).
4. Signs of Variceal Hemorrhage.

Negative EGD

5. Clean stomach and duodenum, no fresh blood or coffee ground.
6. Upper GI pathology non-causative/ incidental.
7. A low grade non-variceal lesion (Forrest IIc, III).

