#### ***7.3.2 Secondary Outcomes***

Our secondary objective is to estimate the sensitivity and specificity of VCE compared to subsequent EGD in the detection of serious bleeding lesions in the upper gastrointestinal (GI) tract.

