### **11.3 Final Analysis Plan**

The analysis will be conducted in several stages. First, we will compare the baseline characteristics of the two study groups to determine if randomization was successful. We will also compare the baseline characteristics of the study samples by enrollment site. Second, we will compare the VCE and EGD results and classify all study subjects according to whether there is a high versus low risk lesion present. The VCE and EGD results may differ because they are not being performed at the same time and GI bleeds can resolve or change so it is unlikely that there will be perfect agreement between the two modalities. In cases where one modality identifies a low risk lesion and the other one a high-risk lesion, we will classify the lesion as high risk. If the VCE could not adequately visualize the tract, we will classify the results according to the EGD. We will compare the sensitivity and specificity of VCE and EGD for identifying high risk lesions. Finally, we will separately compare the admission rates of high-risk lesions and low risk lesions between the two study groups. We will compare admission rates aggregated across the four study centers as well as within each study center.

For tertiary outcomes, we will compare the outcomes by study group using a chi-square test statistic if the outcome is categorical such as the presence of an adverse event and a t test (normally distributed) or median test (non-normally distributed) if the outcome is continuous such as hospital or ED length of stay.

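### Section 11.3 promises sensitivity and specificity for both VCE and EGD with no reference named, and does not keep its either-positive and EGD-fill rules out of the accuracy table

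*Combined protocol and SAP*

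**What the plan says.** Section 3.1 sets the aim: "Our secondary objective is to estimate the sensitivity and specificity of VCE compared to subsequent EGD". Section 3.2.2 repeats it as "Secondary Outcome: Sensitivity and specificity of VCE compared to EGD", item 13 of section 4.4 uses the same words, and section 7.3.2 again plans to "estimate the sensitivity and specificity of VCE compared to subsequent EGD in the detection of serious bleeding lesions". All four make EGD the comparator.

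Section 3.2.2 then lists the findings that make each test positive or negative, and gives VCE a third, inconclusive class: "Any capsule that does not pass the pylorus before battery life is expired (and does not detect lesion in stomach or esophagus". Signs of malignancy are on the positive list for VCE but not on the positive list for EGD.

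The second stage of section 11.3 classifies subjects as having a high- or low-risk lesion using two rules. In cases "where one modality identifies a low risk lesion and the other one a high-risk lesion, we will classify the lesion as high risk". And: "If the VCE could not adequately visualize the tract, we will classify the results according to the EGD". The next sentence is the accuracy analysis: "We will compare the sensitivity and specificity of VCE and EGD for identifying high risk lesions". The admission comparison comes after that, as the final stage.

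**The concern.** The accuracy sentence in 11.3 does not fit the outcome defined elsewhere. A promised sensitivity and specificity of EGD has content only if something other than EGD is the truth, and the only joint truth that 11.3 defines is the either-positive class. That class contains the VCE result, so VCE would be judged partly against itself.

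The EGD-fill rule raises a second problem. A capsule that failed to visualize the tract would be given the EGD answer and then scored as agreeing with EGD, although 3.2.2 sets such capsules apart.

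Two smaller gaps lie alongside. Section 11.3 speaks of high-risk lesions and 3.2.2 of positive tests, and the documents never equate the two. And a non-bleeding tumour seen by both tests is positive on VCE. On EGD it either falls under non-causative pathology, which makes the VCE read a false positive, or it fits neither list.

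At stake is how the only stated secondary outcome is computed, with the choice left open until the data are in hand.

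**Working it through.** **The plan's own figures.** The documents give no target or precision for VCE accuracy, so there is none to reproduce. The one design figure, at least 80% power in 11.2, concerns admission. It reproduces: 100% against 75% with 40 low-risk subjects per arm (80 of 100, assuming 1:1 allocation) gives 93.8% at two-sided 0.05. Nothing below depends on it.

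**Inputs for the illustration.**
- 50 VCE-EGD pairs. Only the experimental arm has VCE (4.4 item 6). The allocation ratio is not stated, so 1:1 is assumed, with every EGD done.
- 20% EGD-positive, the top of the range in 11.2; 10% is also shown. High risk is taken to mean positive.
- VCE sensitivity 95% and specificity 92%, quoted in 2.1 for high-risk lesions. That text names no reference; EGD is assumed. Section 2.1 also quotes 88%/64% against EGD for fresh blood, used as a second case.
- Share of inconclusive capsules f, from 2% ("At 60 minutes, 98% of capsules visualize the duodenum") to about 50% (section 2.1, 20-30 minutes of battery). These are upper limits, because 3.2.2 also requires that no lesion was seen. f is assumed equal in EGD-positives and EGD-negatives.

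**Step 1: the choice of reference, all capsules conclusive.** With 20% EGD-positive there are 10 positives and 40 negatives.
- VCE true positives: 10 × 0.95 = 9.5. VCE-positive but EGD-negative: 40 × 0.08 = 3.2.
- Either-positive class: 10 + 3.2 = 13.2.
- VCE sensitivity: (9.5 + 3.2)/13.2 = 12.7/13.2 = 96.2%.
- EGD sensitivity: 10/13.2 = 75.8%.
- Any positive read on either test puts the subject in the class, so false positives are zero and specificity is 100% for both tests.

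| Case | VCE against EGD | VCE against either-positive | EGD sensitivity against either-positive |
|---|---|---|---|
| 95%/92%, 20% EGD-positive | 95%/92% | 12.7/13.2 = 96.2%, 100% | 10/13.2 = 75.8% |
| 95%/92%, 10% EGD-positive | 95%/92% | 8.35/8.6 = 97.1%, 100% | 5/8.6 = 58.1% |
| 88%/64%, 20% EGD-positive | 88%/64% | 23.2/24.4 = 95.1%, 100% | 10/24.4 = 41.0% |

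The 100% specificity holds for any inputs. The other figures do not.

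**Step 2: inconclusive capsules, EGD as reference.**
- Excluded: 95%/92% for any f.
- Filled from EGD: sensitivity 0.95(1 − f) + f; specificity 0.92(1 − f) + f.
- All counted VCE-positive: sensitivity 0.95(1 − f) + f; specificity 0.92(1 − f).
- All counted VCE-negative: sensitivity 0.95(1 − f); specificity 0.92(1 − f) + f.

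| f | Excluded | Filled from EGD | All VCE-positive | All VCE-negative | Pairs if excluded |
|---|---|---|---|---|---|
| 2% | 95%/92% | 95.1%/92.2% | 95.1%/90.2% | 93.1%/92.2% | 49 |
| 50% | 95%/92% | 97.5%/96.0% | 97.5%/46.0% | 47.5%/96.0% | 25 (5 EGD-positive, 20 EGD-negative) |

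Filling takes its sensitivity from the all-positive bound and its specificity from the all-negative bound. It therefore gives the upper limit of both at once, which no single handling of the capsules as test results can do. With 88%/64% and f = 50%, filling gives 94%/82%.

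**Step 3: malignancy.** No figure can be given. Known gastric cancer is excluded (5.2), so the number of such cases may be zero.

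**The case against.** The strongest reply is that the reference is already settled. Four sections say VCE compared with EGD, and 3.2.2 supplies the endpoint lists, so the sentence in 11.3 is loose drafting. The two rules classify subjects for the admission comparison, and nothing applies them to a two-by-two table. That is a fair reading, and it is why both effects are stated as conditional. But it does not account for a promised accuracy of EGD, and it does not say how inconclusive capsules count. The accuracy sentence sits in the same stage as the rules, before the admission comparison.

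A second reply concerns size. With 10 EGD-positives, 9/10 has an exact 95% interval of about 55% to 100%, and 37/40 for specificity about 80% to 98%. A move from 95% to 96% or 97.5% is well inside that noise, and section 2.1 expects a prokinetic and 60 minutes of imaging to help. This stands for the sensitivity figures and for a low inconclusive share. It does not stand for a specificity fixed at 100% by construction. Nor can the 50% end be dismissed: section 2.1 also describes a capsule that images for 30 minutes.

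Third, lesions can change before EGD, as 4.4 and 11.3 acknowledge, so EGD alone is an imperfect reference. True, and it should be stated as a limitation. A composite that includes the test under evaluation is not a remedy.

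Finally, this version is dated after the planned end of recruitment, so form changes may come too late for subjects already entered. That stands in part. The videos are source data, so capsule reads can be revisited, but a non-bleeding tumour may not have been recorded.

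**Conclusion.** The concern holds and should be fixed. The conflict between 11.3 and sections 3.1, 3.2.2, 4.4 and 7.3.2 is in the text and needs no assumption. Two consequences are algebraic: an either-positive reference fixes specificity at 100% for both tests, and filling from EGD gives the upper bound of sensitivity and of specificity together. Whether either would occur depends on how the analyst reads 11.3.

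The size depends mainly on the share of inconclusive capsules. At 2% the handling moves VCE accuracy by at most about 2 points. At 50% the bounds run from 47.5% to 97.5% for sensitivity and from 46.0% to 96.0% for specificity. These figures rest on the assumed 50 complete pairs, 20% EGD-positive, 95%/92% accuracy and equal inconclusive shares. The percent discharged home, the primary outcome, does not depend on any of this.

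**What to change.** In 11.3:
- State that VCE sensitivity and specificity are estimated against EGD alone, using the positive and negative lists in 3.2.2, and delete the accuracy of EGD.
- State that neither the either-positive class nor the EGD-fill rule enters the accuracy table. This does not endorse the either-positive class for the admission comparison: only the experimental arm has VCE, so the arms would be classified on different information.
- Keep inconclusive VCEs as the class that 3.2.2 defines. Report their number, leave them out of the main estimate, and give the bounds with all counted VCE-positive and all counted VCE-negative.
- Report the interval between VCE and EGD; both dates and times are already recorded.

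In 3.2.2, make the malignancy item the same on both positive lists.

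On the forms (18.9 and 18.10), have tumour recorded whether or not it is bleeding; it now appears only among sources of bleeding. Split item j of the VCE form, which merges passing the pylorus with lesion detection, so that inconclusive capsules can be counted.

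The cost is a few sentences and wording on two forms, with no change in sample size. The price is less flattering results: specificity can fall below 100%, the bounds may be wide, and lesions that resolve before EGD count as VCE false positives, to be stated as a limitation.

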## **11 HYPOTHESIS AND ANALYSIS**

### **11.1 Study Hypotheses**

We hypothesize that there will be no significant difference in the hospital admission rate among subjects diagnosed with a high-risk lesion between the two study groups whereas there will be a significant difference in the hospital admission rate among subjects with a low risk lesion.

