### **11.2 Sample Size Considerations**

With 100 patients, we will have adequate power (i.e.  $\geq 80\%$ ) to detect a 25% difference or greater in admission rates for subjects with low risk lesions with p- value less than 0.05. We assume that the controls will a 100% admission rate. We anticipate 20% or less of all subjects to be diagnosed with a high-risk lesion, we are unlikely to have adequate power to detect a significant difference in the hospital admission rate between the two study groups.

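### Section 11.1 claims that VCE changes admission in low-risk but not in high-risk subjects, yet Section 11.3 tests the two strata separately and never estimates the difference between the two effects

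*Combined protocol and SAP*

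**What the plan says.** Section 11.1 joins two predictions into one hypothesis. For the high-risk stratum it expects "no significant difference in the hospital admission rate among subjects diagnosed with a high-risk lesion between the two study groups". For the low-risk stratum it expects the opposite result: "whereas there will be a significant difference in the hospital admission rate among subjects with a low risk lesion".

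Section 11.2 powers only the low-risk half: "With 100 patients, we will have adequate power" of at least 80% "to detect a 25% difference or greater in admission rates for subjects with low risk lesions with p- value less than 0.05". It adds "We assume that the controls will a 100% admission rate" and "We anticipate 20% or less of all subjects to be diagnosed with a high-risk lesion", and then concedes that "we are unlikely to have adequate power to detect a significant difference in the hospital admission rate between the two study groups". From its position, the concession refers to the high-risk subjects.

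Section 11.3 gives the analysis: "Finally, we will separately compare the admission rates of high-risk lesions and low risk lesions between the two study groups", pooled over centres and within each centre. It names no test for admission rates; chi-square is named only for categorical tertiary outcomes. No interaction test, estimate of the difference between the stratum effects, or interval for that difference appears in the protocol.

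**The concern.** Section 11.1 makes a claim about a difference between two effects: the capsule lowers admission where the lesion is low risk and leaves it unchanged where the lesion is high risk. Two separate tests do not address that claim. A p-value below 0.05 in about 80 subjects and one above 0.05 in about 20 is what two identical effects can produce when one stratum is four times the size of the other. Section 11.2 already expects the smaller test to lack power, so half of the hypothesis may come out as predicted for that reason alone.

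At stake is whether the trial may report that discharge after VCE tracks lesion risk. The primary goal in Section 3.1 is safe discharge of low-risk patients, which presupposes that it does.

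**Working it through.** **Inputs.** From Section 11.2: 100 subjects, high-risk share 20% or less, control admission 100%, a 25-point difference, p below 0.05. Assumed because not stated: 1:1 allocation, two-sided tests, no dropout, equal strata across arms. A 20% high-risk share gives 40 low-risk and 10 high-risk subjects per arm (40/10). A 10% share, also within the stated range, gives 45/5. Because 11.3 names no test for admission, both Fisher's exact test and the uncorrected chi-square are shown.

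**1. The plan's own power figure.** For 100% v 75% the mean proportion is 0.875, so √(2 × 0.875 × 0.125) = 0.4677 and √(0 + 0.75 × 0.25) = 0.4330.

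- Required n per arm for 80% power: (1.96 × 0.4677 + 0.8416 × 0.4330)² / 0.25² = 1.641 / 0.0625 = 26.3, so 27 (34 with continuity correction).
- Power at 40 per arm: Φ[(0.25 × √40 − 1.96 × 0.4677) / 0.4330] = Φ(1.53) = 93.8%. Exact enumeration gives 95.7% (Fisher) and 99.5% (chi-square).

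The statement of at least 80% power in the low-risk stratum is met.

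**2. The high-risk stratum at the same 25-point effect.** Power is 7.8% (Fisher) or 22.4% (chi-square) at 10 per arm, and 1.6% or 10.4% at 5 per arm.

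**3. How often a risk-blind pathway yields the 11.1 pattern.** Let a proportion d of capsule-arm (CERA) subjects go home in both strata, and no controls. Each test then reduces to a threshold on the number sent home in CERA:

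| Per arm | Fisher p below 0.05 from | Chi-square p below 0.05 from |
|---|---|---|
| 40 | 6 (p = 0.026; 5 gives 0.055) | 4 |
| 10 | 5 (p = 0.033; 4 gives 0.087) | 4 |
| 45 | 6 | 4 |
| 5 | 4 | 3 |

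P(pattern) = P(low-risk count reaches its threshold) × P(high-risk count stays below its threshold), both counts binomial with probability d.

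At d = 0.25 with 40/10, Fisher: P(X ≥ 6; 40, 0.25) × P(X ≤ 4; 10, 0.25) = 0.957 × 0.922 = 0.882.

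| Sent home, both strata | 40/10 Fisher | 40/10 chi-square | 45/5 Fisher | 45/5 chi-square |
|---|---|---|---|---|
| 25% | 88% | 77% | 97% | 90% |
| 40% | 63% | 38% | 91% | 68% |
| 60% | 17% | 5.5% | 66% | 32% |
| 81% | 0.5% | 0.1% | 24% | 5% |

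The last row is close to the feasibility trial described in Section 2.1, where 7 of 37 VCE patients were admitted, so 30 of 37 (81%) were not.

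**4. The direct contrast.** With all controls admitted in both strata, the difference between the two arm effects on the risk-difference scale is CERA admission in high-risk minus CERA admission in low-risk subjects. A logistic interaction is not estimable, because the control odds are infinite in both strata. A two-sided Fisher test of the two CERA rates (40 v 10) rejects in about 3% of trials when the pathway ignores risk. At 25% sent home in both strata it rejects in the direction 11.1 predicts in 1.0%. Its power when discharge does depend on risk is:

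| Sent home, low v high risk | 40/10 | 45/5 |
|---|---|---|
| 25% v 0% | 18% | about 0% |
| 60% v 10% | 84% | 43% |
| 75% v 10% | 98% | 85% |

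**The case against.** **Discrimination is partly covered elsewhere.** Sensitivity and specificity of VCE against EGD are the declared secondary outcome (Section 3.2.2) and recur in 11.3. A positive capsule leads to admission (Section 4.4), so the proposed contrast is close to sensitivity plus specificity minus 1. The two differ through admissions for haemoglobin or vital signs and through inconclusive capsules. Missed high-risk lesions are also listed as potential major adverse events (Section 2.3.1). This stands: a reader might infer that the plan cannot show discrimination at all, and the documents do not support that. But accuracy of the reading is not the admission claim in 11.1, and nothing in the plan tests that claim.

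**The 25% case is not a forecast.** Section 11.2 gives 25% or greater as a detectable difference. It would be wrong to say that unequal strata produce the pattern whatever the effect: with 40/10 it nearly vanishes at the feasibility trial's rate. This also stands, although 45/5 still leaves 24% (Fisher) there.

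**The calculation does not use the planned strata.** It treats lesion risk as set independently of VCE. Section 11.3 calls a lesion high risk if either modality does, and a positive capsule leads to admission. Equal discharge in both strata is then a narrower failure than the binomials imply. This stands as a limit on the figures. It also exposes a fault in the planned label: only CERA has VCE, so the label helps build high-risk admission into that arm and is not comparable between arms.

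**The low power is already admitted.** Section 11.2 does concede it, but neither the hypothesis nor the analysis changes as a result.

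**Conclusion.** The point holds in limited form. Section 11.1 asserts a differential effect and 11.3 does not estimate it, so significance in one stratum and non-significance in the other could be taken as confirmation when discharge does not depend on lesion risk. The risk is large at modest discharge rates or with few high-risk subjects, and small at rates like 30 of 37 with 10 high-risk subjects per arm. The figures rest on 1:1 allocation, all controls admitted, two-sided 5% tests, no dropout, and lesion risk set independently of VCE.

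Two stronger conclusions should not be drawn. The declared primary outcome, percent discharged home, is untouched by this point. Nor should 11.1 count as supported only if the interval for the contrast excludes zero: at 25% v 0%, which is perfect discrimination at the plan's own effect size, that rule would succeed in 18% of trials with 40/10 and in almost none with 45/5.

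**What to change.** - **11.3:** add the between-stratum difference in the arm effect on admission, on the risk-difference scale, with an exact 95% CI. With all controls admitted, it is CERA admission in high-risk minus low-risk subjects. Report the high-risk CERA admission proportion with its own exact CI. Keep the planned stratum-by-arm comparisons.
- **Strata for this contrast:** assign risk by EGD in both arms. Outpatient EGDs after discharge may be missed, which would remove discharged subjects selectively. Report the number without EGD by arm and disposition, with a sensitivity analysis for their unknown risk class.
- **11.1:** reword so that the differential claim rests on this estimate and interval, and state that a non-significant result in the high-risk stratum is not evidence of no difference.
- **11.2:** state the contrast's power across high-risk shares, as tabulated above.

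The cost is wording in three subsections and some extra calculation, with no new patients or visits. The downside is a less favourable stated precision. For example, if all 10 high-risk CERA subjects were admitted, the exact lower limit for that proportion would be 0.025^(1/10) = 69%, and with 5 of 5 it would be 0.025^(1/5) = 48%.

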During hospital admission, EGD will be performed on all subjects and hemostasis therapy applied as necessary. The study team decided against mandating that EGD be performed within 24 hours of hospital admission. This is a pragmatic trial. The longer the duration between the inpatient EGD and the ED VCE the greater the likelihood of discrepancy in the findings that may be due to a change in the lesion as part of its natural course or due to treatments delivered. However, the primary objective of the study is not to evaluate diagnostic accuracy of the ED VCE. The study team decided it was more important to enroll subjects in a timely manner than exclude subjects because the inpatient EGD was not completed within 24 hours.

For the experimental CERA group, subjects will be monitored for a minimum of 4 hours after ingestion. VCE will be undergo a formal review after completion of the VCE by a staff gastroenterologist with extensive experience in VCEs of the small bowel, colon, and esophagus. Both research personnel and the gastroenterologist will undergo a capsule training program organized by Medtronic and receive accreditation after the training.

11. Subjects in the experimental arm who have no sign of active bleeding, show no serious endoscopic findings on capsule, and have stable hemoglobin, blood pressure and heart rate for at least 4 hours will be discharged from the ED. Discharged CE patients will be scheduled to have an outpatient EGD within 3 days post discharge. Patients will be instructed to return to the ED sooner if signs of new bleeding develops. The Research Coordinator will facilitate setting up this appointment for the patient.

Any subject in the experimental arm with a positive VCE or a negative VCE but has a drop in Hemoglobin  $\geq 3$  at 4 hours or an elevated HR or low BP will be admitted. A hemoglobin drop between 2 and 3 will NOT automatically transfer patient to active control arm. In these cases, decision to proceed will be up to discretion of treating physician. We anticipate that all admitted patients in the experimental arm will undergo EGD in the hospital (same as AC arm.)

12. Primary Outcome: (1) Percent Discharged Home. Assumption is that 100% of Active Control / standard risk assessment will be admitted.
13. Secondary Outcome: Sensitivity and specificity of VCE compared to EGD

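### The declared primary outcome is Percent Discharged Home for the whole arm, but section 11 hypothesises, powers and compares admission rates by lesion risk, so the contrast that decides the trial is not fixed

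*Combined protocol and SAP*

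**What the plan says.** The outcome sections and the statistical section describe different comparisons.

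- **Outcome.** Section 3.2: "3.2.1 Primary Outcome: (1) Percent Discharged Home. Assumption is that 100% of Active Control (AC) group will be admitted". Step 12 of section 4.4 repeats it: "Primary Outcome: (1) Percent Discharged Home. Assumption is that 100% of Active Control / standard risk assessment will be admitted". Neither limits the outcome to a type of lesion.
- **Objective.** Section 3.1: "Our primary goal is to test whether ED Video Capsule Endoscopy (VCE) is able to safely discharge low risk patients". Section 7.3.1, headed as the primary outcomes, repeats this goal and does not mention Percent Discharged Home.
- **Hypothesis.** Section 11.1 has two parts, both within strata. For high-risk lesions, "there will be no significant difference in the hospital admission rate among subjects diagnosed with a high-risk lesion between the two study groups"; for the rest, "whereas there will be a significant difference in the hospital admission rate among subjects with a low risk lesion".
- **Power.** Section 11.2 claims at least 80% power with 100 patients "to detect a 25% difference or greater in admission rates for subjects with low risk lesions with p- value less than 0.05". It expects at most 20% of subjects to have a high-risk lesion and concedes that a comparison in that group is unlikely to be adequately powered.
- **Analysis.** Section 11.3: "Finally, we will separately compare the admission rates of high-risk lesions and low risk lesions between the two study groups". The next sentence says admission rates will be compared over the four centres combined and within each centre. Tests are named only for the tertiary outcomes.

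Section 11.3 also sets the lesion class. Where capsule and EGD disagree, the lesion counts as high risk. Section 4.4 (step 6) gives the capsule to the experimental arm only.

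**The concern.** Admission and discharge home are essentially complements, so the endpoint is not the difficulty. The population is. Three rules could each be taken as deciding the trial: all randomised subjects (3.2.1), low-risk subjects only (11.2), or both parts of 11.1 together. No order is set among them and none is labelled exploratory.

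The rules score one event in different ways. A subject in the capsule (CERA) arm who has a high-risk lesion and is sent home raises the 3.2.1 outcome, is absent from the low-risk comparison, and counts against 11.1. In a trial about safe discharge, that is the event for which the governing rule most needs to be clear.

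A stratum result should not stand in for the declared outcome, because the strata depend on what happens after randomisation. A capsule finding can move a CERA subject from low to high risk, but it cannot move a control. The two low-risk groups are therefore not selected in the same way, even though the arms were randomised. With the deciding contrast left open, it could be chosen after the data are seen.

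**Working it through.** **Inputs from the documents.** N = 100, control admission 100%, a 25-point low-risk difference, p < 0.05, and a high-risk share of 20% or less (all 11.2).

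**Assumptions, not stated in the plan.** 1:1 allocation; two-sided Fisher exact test; a high-risk share at its 20% ceiling, giving 40 low-risk and 10 high-risk subjects per arm; no control discharged; strata taken as known without error.

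**1. The plan's own figure.** With no control discharged, the smallest number of CERA discharges giving p < 0.05 is:

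- 40 per arm: 6 (6/40 v 0/40, p = 0.026; 5/40, p = 0.055)
- 50 per arm: 6 (6/50 v 0/50, p = 0.027; 5/50, p = 0.056)
- 10 per arm: 5 (5/10 v 0/10, p = 0.033; 4/10, p = 0.087)

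Power for the low-risk comparison is P(X ≥ 6) with X ~ Bin(40, 0.25) = 95.7%. The claim of at least 80% holds.

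**2. Power for the declared outcome.** Whole-arm difference = 0.8 × low-risk discharge + 0.2 × high-risk discharge.

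- The plan's effect with all high-risk subjects admitted: 0.8 × 25 + 0.2 × 0 = 20 points. P(X ≥ 6), X ~ Bin(50, 0.20) = 95.2%.
- P(X ≥ 6) with n = 50 reaches 80% at a difference of 15.4 points.
- A full 25-point whole-arm difference gives 99.3%, but that is not the plan's effect, which is 25 points among low-risk subjects.

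**3. The verdicts can part.** If 4 of 40 low-risk and 2 of 10 high-risk CERA subjects go home, the whole arm is 6/50 (p = 0.027) and the low-risk stratum is 4/40 (p = 0.116). If 4 of 40 and 5 of 10 go home, the whole arm is 9/50 (p = 0.003), low-risk p = 0.116 and high-risk p = 0.033: the declared outcome succeeds while both parts of 11.1 fail. Both tables are illustrations. They send home a larger share of high-risk than of low-risk subjects, the reverse of what triage intends.

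**4. How often.** Let L ~ Bin(40, pL) and H ~ Bin(10, pH) be independent CERA discharges. The whole arm succeeds if L + H ≥ 6, and the low-risk test succeeds if L ≥ 6. Both parts of 11.1 are met if L ≥ 6 and H ≤ 4. Summing the probabilities of the discordant pairs gives:

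| pL / pH | Whole arm v low-risk | Whole arm v both parts of 11.1 |
|---|---|---|
| 25% / 0% | 0% | 0% |
| 25% / 5% | 1.2% | 1.2% |
| 25% / 12% | 2.4% | 2.8% |
| 15% / 15% | 21.3% | 21.9% |
| 80% / 36% | 0.0% | 27.1% |

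With 10% high-risk (45 and 5 per arm), the 21.3% falls to 9.5% and the 27.1% to 6.0%. In the last row all the disagreement comes from the high-risk test reaching significance; the whole-arm and low-risk verdicts agree.

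**The case against.** **The aggregation sentence in 11.3 may be the overall test.** It carries no lesion restriction, so a reader who infers that the primary outcome is never tested goes too far. Coming straight after the sentence that splits by lesion, it most naturally pools over centres. Even if it means an overall comparison, nothing makes it primary. What stands is that the declared outcome is not clearly tested and not identified as deciding.

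**The documents lean to low-risk patients.** The protocol summary, 3.1 and 7.3.1 all speak of discharging low-risk patients, and 11.2 powers that group. Limiting 3.2.1 to low-risk subjects would also make the text consistent. This is a fair point, and choosing the whole arm is partly a matter of judgement. But 3.2.1 and step 12 do not carry the restriction, and the low-risk group is defined after randomisation by information that only one arm has.

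**The large disagreement rates sit away from the plan's figures.** This stands. The plan is sized for a low-risk effect of 25 points or more, and in the feasibility trial cited in section 2.1, 30 of 37 capsule patients (81%) avoided admission. Section 4.4 admits every positive capsule reading. The cited sensitivities of 83% to 95% imply that about 5-17% of positives are missed, not 36%. At 80% low-risk and 5-17% high-risk discharge, the whole-arm and low-risk verdicts agree to within rounding, and the whole-arm result differs from the full 11.1 hypothesis in 0.01-1.7% of trials. Section 2.1 does warn that high-risk lesions were missed when the capsule did not pass the pylorus, so a higher rate cannot be excluded.

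**Conclusion.** The concern holds as a failure to fix the deciding contrast. The outcome named as primary is defined for the whole arm, the statistical section is built on lesion strata, and no sentence connects the two or ranks them.

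Two stronger inferences are not supported. One is that the trial is underpowered: on the assumptions above, 100 patients give about 95% power for either contrast at the plan's own effect. The other is that the conclusions are likely to conflict: under the plan's own scenario they coincide, and with 5-12% of high-risk subjects sent home the whole-arm and low-risk verdicts differ in only about 1-2% of trials. Disagreement becomes material if the low-risk effect is small (21% at 15%/15%). Separately, if high-risk subjects are often sent home, the whole-arm result can succeed while the high-risk part of 11.1 fails (27% at 80%/36%).

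The sizes rest on 1:1 allocation, two-sided exact testing, a 20% high-risk share and no control discharges. The mismatch in the text rests on none of these. It should be corrected, although the likely effect on the result is small.

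**What to change.** In 11.1 to 11.3, name one primary contrast: Percent Discharged Home in all randomised subjects, CERA against Active Control by assigned arm, with a 95% confidence interval and one exact test at two-sided 0.05.

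Restate 11.2 for that contrast. With 50 per arm and no control discharge, 80% power is reached at a difference of about 15.4 points. The existing 25-point low-risk effect, with all high-risk subjects admitted, is a 20-point whole-arm difference with about 95% power.

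Report the low-risk and high-risk admission comparisons as secondary estimates with 95% confidence intervals, and state that they cannot replace the primary result. Say whether the comparison over all centres in 11.3 is meant to be overall or within lesion strata.

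The cost is wording and one restated power figure, with no added patients or data. The small downside is that the low-risk comparison loses its status as the powered hypothesis.
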